13.3 Randomization and Stratification

The randomization will be based on a permuted block of size 4 with stratification by tumor volume (≤ 2 positive cores and $\leq 10\%$ of any biopsy core volume is adenocarcinoma vs. >2 positive cores or $> 10\%$ of any biopsy core volume is adenocarcinoma). The decision was made not to stratify by PO to avoid problems with sparse data. After random permutation of numbers from 1 to 4 in each block, incoming subjects in sequence will be randomized to treatment corresponding to the permuted numbers in sequence according to the following: placebo for odd number and PFE for even number, separately among subjects in the lower and higher tumor volume groups. This process will be repeated after every 4 subjects.

13.4 Primary Endpoint(s)

The primary endpoint of the study is the difference in plasma levels of Insulin-like Growth Factor (IGF)-1 from baseline to end of study (12 months) in subjects undergoing AS for early stage prostate cancer. For the primary comparison, the difference between the placebo group and the PFE group will be tested using a two-sample t-test with normalizing transformation if necessary or Wilcoxon rank-sum test.

13.5 Secondary Objectives

For the secondary objectives, we will compare compliance and toxicities for a once daily oral administration over a 12-month period of time between the PFE and placebo groups. We will compare the modulation of the following biomarkers with response to PFE versus placebo: plasma biomarkers, including IGF-1/IGFBP-3 ratio, total serum PSA and normal and abnormal prostate tissue biomarkers, including PSA, IGFBP-3, apoptosis (CASPASE 3), Ki-67, IGF-1R, 8OHdG and androgen receptor. We will also compare PFE constituents/metabolites for evidence of accumulation (trough levels): ellagic acid, dimethyl ellagic acid, dimethyl ellagic acid glucuronide (DMEAG), urolithin A, urolithin A glucuronide, urolithin B and urolithin B glucuronide between the treatment groups. Serum testosterone levels will also be measured.

For secondary objectives, all measurements and changes in measurements of interest will be summarized by treatment arm (and, if applicable, by visit) with appropriate descriptive statistics. Compliance, in terms of the number of pills missed, will be summarized by treatment arm with descriptive statistics, and tested for imbalance using Wilcoxon rank-sum test. Patient toxicity throughout the study will be summarized in several ways; the presence or absence of any toxicities, worst CTCAE grade, and strongest investigator-defined relationship will all be examined and characterized by treatment arm, and analyzed appropriately (Wilcoxon rank-sum for ordinal data, Fisher's exact test for dichotomous data, and log rank test for time to event data). We will examine the differences between the groups for the change from baseline for serum biomarkers, tissue biomarkers, and PFE constituents/metabolites with the appropriate tests; for dichotomous data we will use Fisher's exact test, for ordinal data we will use Wilcoxon rank-sum test, and for continuous data, and a two-sample t-test with normalizing transformation if necessary or Wilcoxon rank-sum test.

We are also interested in the correlation of the markers and expression data with plasma IGF-1 and serum PSA doubling time. These will be tested with Pearson and Spearman correlation coefficients as appropriate; regression models will be developed to test if there is a significant relationship in the presence of treatment effect. Beyond the correlations with the primary endpoint, we are interested in exploratory analyses of the interplay various markers have with each other, and quantifying the individual contributions each make, along with baseline characteristics toward IGF-1 and PSA doubling time: we are interested in examining the complex pathways associated with the chemopreventive activities. In working toward the goal of obtaining an understanding of these relationships, we will explore the correlations and characterize the relationships among the plasma levels of the various biomarkers, the tissue biomarker measurements in normal and malignant tissue and the levels of genetic expression. Where possible, these analyses will be performed on location-matched pre- and post-treatment tumor and benign cores. When there is not a location match, we will select a post-treatment core from the nearest possible location in the prostate. In all cases, the post-treatment tumor core selected for match analysis will be of the same Gleason grade as the pre-treatment core. In addition to analyzing the expression of the selected biomarkers in pre- post-treatment matched tumor and benign cores, we will further characterize the expression of these markers across the prostate by analyzing all biopsy cores that contain cancer. Statistical techniques that may be used include, but are not limited to, Pearson and Spearman correlation analysis and multivariate regression techniques with possible transformation of the data if necessary.

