1. OBJECTIVES

1.1. Primary Objective:

The primary objective of the study is to determine the effect of Pomegranate Fruit Extract (PFE) 1000mg, taken daily for 1 year, on the plasma levels of Insulin-like Growth Factor (IGF-1) from baseline to end of study (52 weeks) in participants undergoing Active Surveillance (AS) for early stage prostate cancer.

1.2. Secondary Objectives:

- 1.2.1. To assess compliance with a once daily oral administration of PFE versus placebo over a 52-week period of time.
- 1.2.2. To assess the toxicity of PFE vs. placebo when taken daily for 52 weeks (+/- 1 week).
- 1.2.3. To compare and correlate the effect of 52 weeks of daily dosing with PFE vs placebo on the end of study biopsy results including the presence or absence of tumor, the extent of tumor and Gleason scores.
- 1.2.4. To compare and correlate biomarker modulation in response to PFE versus placebo in three areas of interest: tissue from a completely benign biopsy core, tumor tissue from a positive core, and normal tissue adjacent to tumor from a positive core. The following biomarkers will be analyzed:
 - Plasma: Insulin-like growth factor 1/IGF binding protein 3 ratio (IGF-1/IGFBP-3 ratio)
 - Prostate tissue (normal and abnormal). In order of priority:
 - apoptosis (CASPASE 3)
 - Ki-67
 - 8OHdG
 - IGF-1R
 - Androgen receptor
 - IGF-1
 - IGFBP-3
 - PSA
- 1.2.5. Measure PFE constituents/metabolites in plasma and urine for evidence of accumulation (trough levels): ellagic acid, dimethyl ellagic acid, dimethyl ellagic acid glucuronide (DMEAG), urolithin A, urolithin A-glucuronide, urolithin B and urolithin B-glucuronide.
- 1.2.6. Measure PSA doubling time (PSA DT) in serum, using the calculation provided on the Memorial Sloan Kettering Cancer Center website: nomograms.mskcc.org/prostate/psadoublingtime.aspx
- 1.2.7. To assess the feasibility of cancer chemoprevention trials in a population of men undergoing active surveillance for prostate cancer.

1.2.8. Measurement of serum testosterone.

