5.3 Run-in Procedures

There is no run in phase for this study.

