7. CLINICAL EVALUATIONS AND PROCEDURES

7.1 Schedule of Events

Evaluation/Procedure	Baseline	Randomization	Week 13 (+/- 1 week) ¹	Week 26 (+/- 1 week) ¹	Week 39 (+/- 1 week) ¹	Week 52 ± 1 Week (or end of study therapy) ¹
Informed consent	x					
Registration	x					
Eligibility Criteria Review	x					
Medical History	x					
Physical Exam	x			x		x
Vital Signs (Temp, BP, Pulse, Respirations) and Weight	x		x	x	x	x
Height	x					
ECOG Performance Status	x					
Assess baseline symptoms	x					
Eligibility/Safety Labs ²	x		x	x	x	x
Total PSA ³	x		x	x	x	x
Randomization		x				
Dispense study medication and diary		x ⁴	x	x	x	
Pill count and drug calendar review			x	x	x	x
Review concomitant medications	x		x	x	x	x
Assess adverse events						x
Prostate Biopsy	x ⁵					x ⁶
The samples listed below will be collected locally, and shipped to UWI for analysis:						
Collect one 3ml red top ⁷	x		x	x	x	x
Collect a second 3ml red top ⁷	x			x		x
Two 10ml green tops ⁷	x		x	x	x	x
Urine collection ⁷	x		x	x	x	x
IHC analysis of normal and abnormal prostate tissue biomarkers (PSA, IGF-1, IGFBP-3, apoptosis [CASPASE 3], Ki-67, IGF-IR, 8OHdG and androgen receptor)	x ⁸					x ⁹

¹The participant must delay his dose of study medication until after blood and urine has been collected, as PK levels need to be assessed approximately 24 hours following the last dose of study medication.

²The following lab tests are to be performed: WBC, Hemoglobin, Platelets, Alkaline Phosphatase, ALT, AST, Total Bilirubin, Serum Creatinine, Sodium, Potassium, Chloride, and Bicarbonate. Eligibility labs must be done \leq 30 days of randomization.

³This total serum PSA will be performed at the PO's clinical lab, and used for clinical purposes.

⁴If the participant is unwilling or unable to return to clinic to pick up study medication, it may be sent overnight by a courier service such as UPS or Fed-Ex.

⁵ The baseline biopsy must have occurred within 13 months prior to the baseline study visit.

⁶The end of study biopsy performed during week 52 ± 1 week or when participant discontinues study therapy. Participant must take study drug the morning of the biopsy after research blood and urine collection but prior to the biopsy.

⁷These blood and urine samples will be used to determine study objectives (PK and biomarker results) as described in §1.2. See §10.2 for collection and processing instructions.

⁸Tissue will be from a biopsy performed within 13 months of study entry

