10.2 Collection and Handling Procedures

At the baseline visit, we will be performing blood and urine pharmacokinetic analyses, plasma biomarker analyses, and total serum PSA and testosterone levels. Pharmacokinetic analyses, plasma biomarker analyses and total serum PSA levels will be done at all subsequent visits. Serum testosterone levels will be done at baseline and Weeks 26 and 52.

To collect the urine specimen: One (1) urine collection cup and four (4) cryovials are required. Collect at least 10 ml of urine. If the participant has difficulty voiding 10 ml of urine, then collect all of the urine the participant can void at one time. You do not need to collect urine from multiple voids to meet the required minimum volume (10ml). Document the date and time of the void, the void volume and the date and time of the previous void.

To process the urine specimen: Aliquot urine into four (4) cryovials. Dispose of any additional urine. Label the tubes with the participant's initials, PID, sample type, time and date of collection.

To store the urine specimen: Freeze the specimens at -70°C . Store the specimens at -70°C until the participant has completed all of the study visits. See section 10.3 for shipping procedures.

To collect the blood specimens: Basic phlebotomy supplies will be in the lab kit provided by the CP lab: green and red top tubes and cryovials as needed. Draw 9mls of blood into each of the green top tubes. Draw 2.5mls of blood into the red top tube(s).

To process the blood specimens: Centrifuge the green top tubes at $\sim 1000\times\text{G}$ for 10-15 minutes. Aliquot the plasma into eight (8) cryovials. Allow the red top tube(s) to clot, then centrifuge at $\sim 1000\times\text{G}$ for 10-15 minutes. If one red top tube is drawn,

aliquot serum equally into two (2) cryovials. If two red top tubes are drawn, aliquot serum equally into four (4) cryovials.

Label cryovials with subject initials, PID, time and date of collection, and sample type (i.e., “baseline” or “Week 13 Visit”, etc.) Freeze at -70° C.

To store the blood specimens: Store the cryovials at -70°C until the participant has completed all of the study visits. See section 10.3 for shipping instructions.

Prostate biopsy specimens:

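### The accumulation objective is tested by a PFE-versus-placebo contrast, which measures trough exposure and cannot separate build-up from carry-over of the last dose

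*Combined protocol and SAP*

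**What the plan says.** Objective 1.2.5 reads "Measure PFE constituents/metabolites in plasma and urine for evidence of accumulation (trough levels", followed by seven analytes; Section 13.1 repeats the aim. Section 13.5 turns it into an analysis: "We will also compare PFE constituents/metabolites for evidence of accumulation (trough levels". That sentence ends "urolithin B and urolithin B glucuronide between the treatment groups", so the contrast is PFE against placebo. The test comes later in the same section: "We will examine the differences between the groups for the change from baseline for serum biomarkers, tissue biomarkers, and PFE constituents/metabolites", using a two-sample t-test, Wilcoxon rank-sum or Fisher's exact test according to data type. Visit-level handling is descriptive only: measurements will be "summarized by treatment arm (and, if applicable, by visit) with appropriate descriptive statistics".

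On sampling, footnote 1 of the Section 7.1 schedule says "PK levels need to be assessed approximately 24 hours following the last dose of study medication". Section 10.2 has pharmacokinetic samples at baseline and adds "Pharmacokinetic analyses, plasma biomarker analyses and total serum PSA levels will be done at all subsequent visits", which means weeks 13, 26, 39 and 52. Section 5.3 states "There is no run in phase for this study", so nothing is sampled early in dosing. Sections 4.1.7 and 5.4 bar other pomegranate intake in both arms.

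Nowhere does the plan define an accumulation ratio, a test across visits within the PFE arm, or a criterion for concluding that accumulation occurred.

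**The concern.** Accumulation is a statement about repeated dosing: the level before the next dose is higher after many doses than after one. It is a contrast over time among men taking the product. The planned test contrasts men taking the product with men who are not, against a baseline drawn before anyone has been dosed.

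A positive result is therefore expected whenever some metabolite survives the 24 h dosing interval, even without build-up. Section 2.2.2 itself reports urinary urolithins persisting for 48 h after a single dose, so a 24 h urine sample could separate the arms on carry-over from the last dose alone. Because Section 13.5 attaches accumulation to this contrast, its wording would allow an exposure finding to be written up as an accumulation finding.

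**Working it through.** **1. The plan's own figure.** Section 13.2 gives 14 per group for the IGF-1 endpoint, two-sided 0.05. Exact two-sample t-test power at n = 14 is 0.800 for 1.10 SD and 0.846 for 1.17 SD. Dropout: 14 / (1 - 0.05) = 14.7, rounded up to 15. These reproduce. No figure is given for the metabolites, so 14 per arm is carried over.

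**2. What the contrast estimates.** On the log scale, with week 52 as the final visit,

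D = (PFE week 52 - PFE baseline) - (placebo week 52 - placebo baseline).

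Neither baseline contains study product, so D is the log ratio of the PFE trough to background. The week-13 value does not enter D, so D is the same whether troughs reached that level by rising, staying flat or falling.

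**3. Can D be split into carry-over and build-up?** Take a one-compartment model with 24 h dosing. The steady-state trough is the 24 h residue of one dose multiplied by R = 1 / (1 - exp(-24k)), where k = ln 2 / half-life. Days to 99% of steady state are ln(100) / (24k). The documents give no half-lives, so a range is assumed:

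| Assumed half-life | R | Days to 99% of steady state |
|---|---|---|
| 4 h | 1.02 | 1.1 |
| 6 h | 1.07 | 1.7 |
| 12 h | 1.33 | 3.3 |
| 24 h | 2.00 | 6.6 |
| 48 h | 3.41 | 13.3 |

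D contains the product of residue and R. Separating them needs a 24 h sample after the first dose, and none is scheduled. The first on-treatment sample is at about day 13 × 7 = 91, past steady state in every row, so the week-52/week-13 ratio is expected to be about 1.00 throughout, including where R is 3.41.

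**4. How often the planned test is significant with flat troughs.** Simulation of 20,000 trials, 14 per arm, log scale, PFE troughs equal in expectation at weeks 13 and 52. Between-man/within-man SDs are assumed. The between-arm test is a two-sample t-test on change from baseline.

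| PFE trough / background | SDs 0.5/0.5 | SDs 0.8/0.6 |
|---|---|---|
| 1.5 | 31.4% | 23.2% |
| 2 | 70.8% | 55.1% |
| 3 | 97.8% | 91.3% |
| 5 | >99.9% | 99.8% |
| 10 | 100% | 100% |

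A paired week-13 to week-52 test within PFE rejects in 4.8-5.2% throughout, as it should for a null of no change between those visits.

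**5. What a within-PFE test can detect.** With 14 men, a paired test has 80% power for 0.81 SD of the within-man difference. That SD is √2 × within-man SD:
- within-man SD 0.5: 0.81 × 0.707 = 0.573, and exp(0.573) = 1.77;
- within-man SD 0.6: 0.81 × 0.849 = 0.687, and exp(0.687) = 1.99.

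Only a rise of roughly 1.8- to 2-fold between weeks 13 and 52 would be found reliably.

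**The case against.** The best defence is that this is a 30-man exploratory study, that 1.2.5 says measure rather than test, and that by-visit summaries would let a reader see a trend in the PFE arm. Trough timing also gives the arm contrast real content. All of this limits the point. None of it removes the mismatch: Section 13.5 names a between-arm test for accumulation, and nothing ties the descriptive summaries to a conclusion.

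Several stronger readings are tempting but not supported.

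- *A difference shows only that men swallowed capsules.* It shows more: metabolite persisting about 24 h after a dose, which is a precondition for accumulation.
- *Any detectable exposure makes the test significant.* That requires placebo levels near zero, which the documents do not establish. Only pomegranate is barred. Section 6.1 calls punicalagin unique to pomegranate, but it is not among the seven analytes. The extract study in Section 2.2.2 used a polyphenol-free diet beforehand. With background present, the rate at a twofold trough is 55-71%.
- *Flat troughs from week 13 to 52 mean no accumulation, so the scheduled samples can settle the question.* Step 3 shows otherwise: more than threefold build-up could be complete before week 13.
- *Time since last dose is not captured.* Section 7.2.12 has the diary record the date and time of each dose, and Section 10.2 has tubes labelled with collection time and date.

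**Conclusion.** The mismatch stands. The planned contrast measures trough exposure; it is not evidence of accumulation, and no other analysis in the plan supplies that evidence. That conclusion follows from the text and does not depend on the simulation.

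The size does depend on assumptions. With flat troughs, the planned test is significant in 55-71% of trials at twice background, 91-98% at three times and over 99% at five times or more, under the two assumed SD pairs. The steady-state argument assumes one-compartment kinetics and half-lives of 4 to 48 h.

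A reader might infer that the sponsor will misreport exposure as accumulation. The documents do not show that; they show only that the wording permits it. The primary IGF-1 analysis is unaffected.

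**What to change.** 1. In Section 13.5, label the between-arm comparison as a check on trough exposure, adherence and dietary contamination, and state that it will not be reported as accumulation.
2. Reword 1.2.5, 13.1 and 13.5 to steady-state trough exposure and its trend over time. With no sample after the first dose, an accumulation ratio cannot be estimated.
3. Within the PFE arm, model log trough at weeks 13, 26, 39 and 52 with a time trend and a random participant effect, or report the week-52/week-13 ratio with its 95% CI. Derive time since last dose from diary and tube times; it will vary, since Section 5.6 allows alternate-day dosing. State how values below the assay limit are handled.
4. State that this analysis tests only continued rise after week 13, and that a flat trend does not exclude build-up before then.

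The cost is wording plus one exploratory model per metabolite, with no new samples. The downsides are low power with about 14 men (80% only for about 0.81 SD of the within-man difference) and a more modest stated objective.

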5.6 Dose Modification

The study drug dose modification schema is as follows:

IF	THEN
The participant experiences a grade 2 adverse event that is possibly, probably, or definitely related to study drug	Stop study drug temporarily for up to 4 weeks.
The adverse event resolves to \leq grade 1 within 4 weeks:	Re-start study drug at 50% dose reduction (1 capsule should be administered every other day).
If the adverse event does not resolve to \leq grade 1 within 4 weeks:	Stop study drug permanently. Continue to follow participant per the schedule of events in Section 7.1, if participant is willing.
If the participant experiences a grade 2 event after initial dose reduction, and the adverse event is possibly, probably or definitely related to study drug:	Stop study drug permanently and follow until the adverse event is resolved to \leq grade 1. Continue to follow participant per the schedule of events in Section 7.1, if participant is willing.
In the event a subject had study drug stopped while on the 50% dose reduction, for a grade 2 adverse event that is NOT possibly, probably or definitely related to study drug	Stop study drug temporarily for up to 4 weeks. If the adverse event resolves to \leq grade 1 within 4 weeks, re-start study therapy at the 50% dose reduction level. If the adverse event does NOT resolve to \leq grade 1 within 4 weeks, permanently discontinue study drug. Continue to follow participant per the schedule of events in Section 7.1, if participant is willing.
A grade 3 or 4 adverse event occurs, regardless of relationship to study drug	Stop study drug and call protocol chair to determine if and when drug should be re-started.

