5.7 Adherence/Compliance

- 5.7.1 Ideally, participants will receive 52 ± 1 weeks of treatment. The required compliance rate for evaluability is $\geq 80\%$. Doses that are missed due to drug holidays (as described in Section 5.6) will not count as non-compliance.
- 5.7.2 The participant's compliance will be measured by evaluating study calendars and pill counts. Participants will be informed, both verbally and in writing at all visits of the following important compliance points:
- Bring all bottles of study drug (whether or not there is medication in the bottle) to study visits.
 - Bring completed pill diary to study visits.

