7.3.1.5 Compliance Assessment

The participant's compliance with study agent dosing will be assessed at each visit. The compliance rate is determined using the following calculation: $\frac{\text{The number of capsules dispensed} - \text{the number of capsules returned}}{\text{the number of capsules taken in a period}} = \text{the number of capsules taken in a period} \div \text{the number of capsules prescribed for that period} \times 100 = \% \text{ compliance}$. The pill diary will be reviewed with the participant to ensure that any missed doses and the reason for the missed dose is documented. A participant must have $\geq 80\%$ compliance to be evaluable for this study. If the participant is having issues with compliance, the importance of taking study agent as prescribed and strategies to improve compliance will be discussed with the participant and documented in the visit notes.

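### Section 13.5 tests compliance as a count of missed pills with no denominator, so the comparison mixes time on agent with adherence

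*Combined protocol and SAP*

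**What the plan says.** Comparing compliance between PFE and placebo over 52 weeks is secondary objective 1.2.1. Section 13.5 names the variable and the test: "Compliance, in terms of the number of pills missed, will be summarized by treatment arm with descriptive statistics", and the arms are "tested for imbalance using Wilcoxon rank-sum test". It gives no denominator and no exposure period, and no rule for capsules after a permanent stop, during a holiday or on a reduced schedule.

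Other sections treat compliance as a rate:

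- Section 7.3.1.5: "The compliance rate is determined using the following calculation". Capsules taken (dispensed minus returned) are divided by "the number of capsules prescribed for that period" and multiplied by 100. This is assessed at each visit.
- Section 5.7.1: "The required compliance rate for evaluability is" at least 80%, and "Doses that are missed due to drug holidays (as described in Section 5.6) will not count as non-compliance".

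The number of capsules prescribed can differ between men. Section 5.6 provides for a holiday ("Stop study drug temporarily for up to 4 weeks"), a reduced schedule ("Re-start study drug at 50% dose reduction (1 capsule should be administered every other day") and a permanent stop with continued follow-up if the man is willing. Section 8.3 lists further reasons for stopping agent. Section 13.6 leaves out only obvious random dropouts and men who never took treatment, so other early stoppers stay in the analysis. It also keeps pill-count information out of the primary analysis.

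**The concern.** The sites calculate a percentage, but the analysis section tests a count. The two rank men alike only if everyone is prescribed about the same number of capsules, and the protocol allows for cases where they are not. Early stopping can follow adverse events, so it may differ by arm. The Wilcoxon test on the count could then show an arm difference that reflects time on agent, or hide a real difference in adherence. A reader of the report could not tell which.

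**Working it through.** **Plan's own figure.** None is given for compliance. The only sample-size figure is for IGF-1: 14 per group, and 14/0.95 = 14.7, rounded up to 15. That reproduces, and 15 per arm is used below.

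**Inputs from the documents.** Planned treatment is 364 days (8.3) at one capsule a day (5.1). Week 13 is day 91.

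**Assumptions not in the documents.** The stop week, the number of stoppers and the adherence levels.

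**Step 1: two ways to count.** Missed to stop date = prescribed while on agent − taken. Missed against full course = 364 − taken.

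| Man | Prescribed | Taken | Missed to stop date | Missed against 364 | 7.3.1.5 percentage |
|---|---|---|---|---|---|
| Stops week 13, misses 20% | 91 | 72.8 | 18.2 | 291.2 | 80% |
| Completes, misses 5% | 364 | 345.8 | 18.2 | 18.2 | 95% |
| Stops week 13, takes 64 | 91 | 64 | 27 | 300 | 70.3% |
| Completes, takes 328 | 364 | 328 | 36 | 36 | 90.1% |
| Stops week 13, misses none | 91 | 91 | 0 | 273 | 100% |

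(91 × 0.20 = 18.2; 364 × 0.05 = 18.2; 364 − 72.8 = 291.2.)

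To the stop date, the man at 70.3%, who is below the 80% threshold, ranks as more compliant than the completer at 90.1% (27 missed against 36). Against 364 the order reverses, and even a perfect taker who stops at week 13 has 273 missed. The distortion changes direction with the definition, and 13.5 does not choose one.

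**Step 2: holidays and alternate-day dosing.** A man who takes every capsule, has a holiday in weeks 13 to 17 and then doses on alternate days is prescribed 91 + 123 = 214 and takes 214. Under 5.7.1 and 7.3.1.5 he has 0 missed and 100% compliance. Only a count against 364 gives him 364 − 214 = 150 missed.

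**Step 3: effect on the test.** Simulation with 15 men per arm, the same adherence distribution in both arms (mean 90%, Beta(18,2), or mean 92%), week-13 stoppers in one arm only, and a two-sided Wilcoxon test at 0.05. Rejection rates over repeated runs of 2,000 to 10,000 trials:

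| Stoppers in one arm | Count to stop date | Count against 364 | Percentage of prescribed |
|---|---|---|---|
| 1 of 15 | 4–5% | 4–5% | about 5% |
| 2 of 15 | about 6% | about 7% | 4–5% |
| 3 of 15 | about 9% | about 11% | 4–5% |
| 5 of 15 | 18–21% | 27–29% | about 5% |

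If stopping is equally likely (10%) in both arms, the count rejects in 4.6%. With 3 of 15 men on alternate-day dosing from week 13, it rejects in about 5% to 6% against prescribed capsules and about 10% to 12% against 364.

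**The case against.** The strongest reply is that 13.5 should be read with the rest of the protocol. It analyses compliance, and 5.7.1 says which doses do not count as non-compliance. An off-day capsule on the reduced schedule was never prescribed, so on the 7.3.1.5 basis it cannot be missed. This stands. A reader might infer that the planned test makes men on protocol-directed holidays or alternate-day dosing look non-compliant. The documents do not support that: it happens only if the analyst departs from 5.7.1 and 7.3.1.5. What remains is that 13.5 does not cite them.

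Second, three stoppers in one arm and none in the other may be unlikely. If each man stopped with probability 5%, the planned dropout rate in 13.2, the chance of 3 or more of 15 in a given arm is 1 − (0.463 + 0.366 + 0.135) = 0.036. Multiplying by 0.463 for none in the other arm gives about 1.7%, or 3.4% for either arm. Section 6.2 reports gastrointestinal events in under 2% at 1000 mg. This limits the expected size. However, the 5% refers to random dropout, which 13.6 excludes, and the plan gives no rate for stopping agent while staying in follow-up.

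Third, the 0.05 level is set for the primary comparison only and the study calls itself exploratory. Objective 1.2.1 covers 52 weeks, so early stopping is arguably part of the outcome. This also stands. It is a reason to report time on agent in its own right; it does not justify merging it with adherence in one undefined count.

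**Conclusion.** The concern holds in a limited form. Section 13.5 names a test variable without a denominator although 7.3.1.5 already supplies one, and the count mixes time on agent with adherence under either reading. The arithmetic in Step 1 needs no assumption about how many men stop.

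The effect on the test does. It is about 9% to 11% rejection, against 4% to 5% for the percentage, if 3 of 15 men in one arm only stop at week 13 with equal true adherence. With one or two stoppers, or with balanced stopping, there is little or no inflation. A reader might take 9% to 11% as the error rate of the planned test; the documents give neither a stopping rate nor an alpha for this comparison, so the figures are illustrative. Nor do they support a fixed direction, since early stoppers look better or worse depending on the definition.

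The primary IGF-1 analysis and the sample size are unaffected. The change is worth making because it is nearly free.

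**What to change.** In 13.5, replace the number of pills missed by percent compliance as calculated in 7.3.1.5, taken over each man's period on agent. Apply 5.7.1 to holiday doses, and use the schedule actually prescribed under 5.6 as the denominator. Cite those three sections. Keep the Wilcoxon rank-sum comparison. Because the objective covers 52 weeks, report time on agent and early discontinuation by arm as separate summaries.

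The cost is a short change of wording and one extra summary. The percentage is already assessed at each visit, so no new data are needed, and no dosing or clinical rule changes.
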